**Table 6-1 Study calendar- On-treatment evaluations**

Study Day	Screening	52-Week Double-Blind Treatment Period Days 0-364 (Weeks 0-52)														Post-Treatment Follow-up Period		
		Day 0 visit	Day 14 visit ± 3 days	Day 28 visit ± 3 days	Day 56 visit ± 7 days	Day 84 visit ± 7 days	Day 112 visit ± 7 days	Day 140 visit ± 7 days	Day 168 visit ± 7 days	Day 196 visit ± 7 days	Day 224 visit ± 7 days	Day 252 visit ± 7 days	Day 280 visit ± 7 days	Day 308 visit ± 7 days	Day 336 visit ± 7 days	Day 364/ EXIT (4-wks post dose) A, J ± 7 days	Post-txt f-up for non-completers ± 7 days	8-week Follow-up B ± 7 Days
Study Week		Wk 2	Wk 4	Wk 8	Wk 12	Wk 16	Wk 20	Wk 24	Wk 28	Wk 32	Wk 36	Wk 40	Wk 44	Wk 48	Wk 52	4 wks post last dose		X
Immunogenicity M		X			X				X									X
B cells		X			X				X									X
Pharmacogenetic Sampling M		X																
BLyS Protein		X																
ANA	X	X																
Complement (C3/C4) and anti-dsDNA	X	X		X	X	X	X	X	X	X	X	X	X	X	X			
Extractable nuclear antigens (ENAs) O		X			X				X									X
Anti-phospholipid antibodies (aCL, lupus anticoagulant, ±beta-2-glycoprotein-1) O		X			X				X									X
Serum IgA, IgM, IgG	X	X			X		X		X		X		X		X			X
IV Administration of Study Agent P																		
		X	X	X	X	X	X	X	X	X	X	X	X	X				

**Table 6-1      Study calendar - On-treatment evaluations (footnotes)**

Refer to Section 6.1 for a list of assessments required for screening/eligibility.

- A The Exit (Day 364) visit will occur approximately 4 weeks after the last dose of study agent. For subjects completing all 48 weeks of treatment and continuing into the 6-month open-label extension, this visit will also serve as their 1st (ie, Day 0) visit of the 6-month open-label extension (see Table 6-2). For subjects who discontinue study agent prior to Week 48, the Exit (Day 364) visit should be performed 4 weeks after the last administration of study agent and a follow-up visit 8 weeks after the last administration of study agent, and a survival assessment (eg, by phone contact) will take place approximately 52 weeks after the first dose of study agent (see Footnote N).
- B The 8-week follow-up visit is to occur approximately 8 weeks after last dose of study agent for subjects withdrawing early and those subjects who do not continue into the 6-month open-label extension.
- C Must be completed by the subject prior to any study-related discussion with the investigator or study coordinator. The FACIT-Fatigue Scale will only be completed by subjects for whom a survey exists in the subject's language.
- D Weight should be obtained prior to dosing at each visit to calculate the dose to be administered. At sites where it is impractical to use the subject's current body weight to calculate the dose, it is permissible to use the subject's body weight from the previous visit. However, the subject's body weight will be measured prior to dosing and if the previous visit weight and current visit weight vary by more than 10% then the weight measured at the current visit must be used.
- E Refer to Appendix 10 for a listing of laboratory assessments to be completed. PT/PTT will be assessed according to the separate line item for PT/PTT in this table.
- F A 24-hour urine may be done if clinically indicated (eg, renal flare).
- G Serum pregnancy test required at screening. Results of urine pregnancy test at subsequent visits, if required, must be available prior to dose. See Section 6.1 (Screening Procedures) for definition of those exempted from subsequent pregnancy testing. Women of child-bearing potential must be reminded of the requirement to report any pregnancy that occurs through 16 weeks following the last dose of study agent (see Section 7.6).
- H Pharmacokinetic sampling: Before the start of infusion on Days 0, 56, and 364 (only if continuing into the 6-month open-label extension); 0-4 hours after the end of infusion on Days 14 and 168; at any time during the visit during the 8-week follow-up visit.
- I C-SSRS Since Last Visit form (see Appendix 4) will be used at Day 0 and all subsequent visits. The C-SSRS Baseline/Screening form (see Appendix 3) is only used at Screening.
- J Study agent is to be administered only if the subject is continuing into the 6-month open-label extension, and this dose will be the 1st dose in the 6-month open-label extension. The dose should not be administered until the completion of all Day 364/Week 52 assessments.
- K SLE Disease Activity Scales: SELENA SLEDAI, SLE Flare Index, BILAG, and PGA. Refer to Section 6.8.1 for guidelines for scoring proteinuria for SELENA SLEDAI evaluation.
- L Unscheduled Visits: Other assessments may be performed as clinically indicated.
- M Pharmacogenetic (PGx) sampling should be drawn at baseline (Day 0); however, the sample can be taken at any time point during the study. Informed consent must be obtained prior to any blood being taken for PGx research. Samples should be drawn prior to dosing.
- N Subjects who discontinue study agent treatment at any time during the study will have a survival assessment (eg, by phone contact) approximately 52 weeks after the first dose of study agent. In the event that a subject withdraws consent, an attempt should be made at the time of consent withdrawal to obtain consent for survival status at Week 52.
- O Will be measured in all subjects at Day 0 and samples will be collected at the time points specified; however, the assay will be run only on subjects with elevated titers of these antibodies.
- P Subjects should remain under clinical supervision for 3 hours after completion of the first 2 study agent infusions. Should symptoms of acute hypersensitivity occur, an extended period of monitoring may be appropriate, based on clinical judgment.

(concluded)

#### **6.4. 6-Month Open-Label Extension**

Subjects who complete the initial 52-week double-blind treatment period may choose to enter into a 6-month open-label extension. The Day 364/Week 52 visit from the 52-week double-blind treatment period will serve as the Day 0 visit for subjects entering the 6-month open-label extension. Subjects on active drug or placebo will receive belimumab 10 mg/kg IV approximately every 28 days for 6 months in the open-label extension. The 1st dose on the 6-month open-label extension will be given on Day 364 (Week 52) of the double-blind treatment period after the completion of Day 364 (Week 52 assessments) (see [Table 6-2](#) for schedule of evaluations). All subjects should remain under clinical supervision for 3 hours after completion of the first 2 infusions. Should symptoms of acute hypersensitivity occur, an extended period of monitoring may be appropriate, based on clinical judgment.

All subjects participating in the open-label extension will continue to be monitored for efficacy and safety as per the study calendar (see [Table 6-2](#)).

During the 6-month open-label extension, the investigator may adjust concurrent medications (add, eliminate, change dose level/frequency) as clinically appropriate. Investigators are encouraged to consider the guidance provided in Section [5.5.1.2](#) regarding corticosteroid reduction during periods of stable SLE disease. The American College of Rheumatology ([ACR](#)) draft guidance regarding steroid dosing and tapering in response to SLE flare is provided in [Appendix 6](#). The reason for altering any immunosuppressant therapy (eg, toxicity associated with the medication, fluctuations in disease activity, etc) must be recorded in the source documentation. Prohibited medications as outlined in Section [5.5.2](#) will still apply.

All subjects will return for an Exit visit approximately 4 weeks after their last dose of study agent as well as a follow-up visit approximately 8 weeks after the last dose of study agent. These visits apply to subjects who have completed as well as those who have withdrawn early from the open-label extension.

After the 6-month open-label extension phase, subjects who wish to continue treatment may do so by being prescribed commercially available belimumab. If belimumab is not commercially available in a subject's country of participation, the subject may continue to receive belimumab under a separate continuation protocol. A separate informed consent will need to be provided for the continuation protocol. The 8-week follow-up visit is not required for subjects entering the continuation protocol.

**Table 6-2 Study calendar 6-month open-label extension**

Study Day	Day 0 visit (Week 52/Exit Visit On-Treatment Phase) a	Day 28 visit ± 7 days	Day 56 visit ± 7 days	Day 84 visit ± 7 days	Day 112 visit ± 7 days	Day 140 visit ± 7 days	Day 168 visit ± 7 days	Day 196/EXIT (4 weeks post last dose) ± 7 days	8-week Follow-up (8 wks post last dose) + 7 Days
Study Week	Day 0	Wk 4	Wk 8	Wk 12	Wk 16	Wk 20	Wk 24	Wk 28	
IV administration of study agent h	X	X	X	X	X	X	X		
Clinical Assessments:									
Weight d		X	X	X	X	X	X		
Symptom-driven Physical Exam									
C-SSRS Since Last Visit									
Assess/Record Adverse Events		X	X	X	X	X	X	X	
Record all current medications		X	X	X	X	X	X	X	
SLE Disease Activity Scales						X	X e		
SLICC/ACR Damage Index							X		
FACIT-Fatigue Scale g							X		
Laboratory Assessments:									
Labs: Hematology & Modified Chem 20 (non-fasting)						X	X e	X	
PT/PTT						X			
Urinalysis						X	X e	X	
Spot urine (protein to creatinine ratio)						X	X e		
Urine Pregnancy Test c	X	X	X	X	X	X	X	X	
Pharmacokinetic Sampling									
Immunogenicity j						X	X e	X	
B cells						X	X e		
Complement (C3/C4) and anti-dsDNA						X	X e		
Extractable nuclear antigens (ENAs)									
Anti-phospholipid antibodies (aCL, lupus anticoagulant, ±beta-2-glycoprotein-1)									
Serum Immunoglobulin IgG, IgA, IgM			X			X	X e		

a Day 0 of the 6-month open-label extension is the Day 364/Week 52/Exit study visit from the On-Treatment phase of the study (see Table 6-1) and represents the first belimumab administration for those subjects continuing in the 6-month open-label extension.

b All subjects, including subjects who have discontinued study agent prior to Day 196, will return for an Exit visit approximately 4 weeks after their last dose of study agent as well as a follow-up visit approximately 8 weeks after the last dose of study agent.

c Urine pregnancy test, as required, with results available prior to dosing. Women of child-bearing potential must be reminded of the requirement to report any pregnancy that occurs through 16 weeks following the last dose of study agent (see Section 7.6).

d The weight at the current visit will be used for calculating the dose. At sites where it is impractical to use the subject's current body weight to calculate the dose, it is permissible to use the subject's body weight from the previous visit. However, the subject's body weight will be measured prior to dosing and if the previous visit weight and current visit weight vary by more than 10%, then the weight measured at the current visit must be used.

- e Assessment to be performed only if assessment was not done at Day 168/Week 24.
- f The 8-week follow up visit is not required for subjects entering the separate continuation protocol.
- g Must be completed by the subject prior to any study-related discussion with the investigator or study coordinator. The FACIT-Fatigue Scale will only be completed by subjects for whom a survey exists in the subject's language.
- h Subjects should remain under clinical supervision for 3 hours after completion of the first 2 infusions. Should symptoms of acute hypersensitivity occur, an extended period of monitoring may be appropriate, based on clinical judgment.

## **6.5. Exit Visit**

Subjects who drop out and do not complete the study will return for an Exit visit 4 weeks after the final dose of study agent.

During the double-blind treatment period, the assessments for the Week 52 visit will be performed for the Exit visit. During the 6-month open-label extension, the assessments for the Week 28 visit will be performed for the Exit visit.

Refer to the Study Calendar ([Table 6-1](#) and [Table 6-2](#)) for a list of procedures required at this visit.

## **6.6. 8-Week Follow-up Visit**

All subjects, except those entering the separate continuation protocol, must return for a follow-up visit approximately 8 weeks after the last dose of study agent.

Refer to the Study Calendar ([Table 6-1](#) and [Table 6-2](#)) for a list of procedures required at this visit.

## **6.7. Unscheduled Visits**

Unscheduled visits may be necessary during the course of the study to capture a subject's status between regularly scheduled visits. Examples include, but are not limited to, a worsening of SLE symptoms, AE reporting, or follow-up to a previously reported AE.

Refer to the Study Calendar ([Table 6-1](#)) for a list of procedures required at these visits. Other assessments as clinically indicated should be performed.

## **6.8. Laboratory Tests**

Non-fasting clinical laboratory tests will be performed as outlined in the Study Calendar (see [Table 6-1](#) and [Table 6-2](#)).

Due to the potential for unblinding, the following lab results will not be provided to study sites after Day 0: aCL (IgM, IgG, IgA isotypes), ENAs (such as anti-Sm, anti-ribonucleoprotein (anti-RNP), anti-Sjögren Syndrome A (anti-SS-A), anti-Sjögren Syndrome B (anti-SS-B), and anti-ribosomal P), serum immunoglobulin isotypes IgM/IgA, and FACS of peripheral lymphocytes.

It has been demonstrated that there is a strong correlation between the protein content of a 24-hour urine collection and the urinary protein:urinary creatinine ratio in a single urine

sample (Ginsberg et al, 1983; Ruggenenti et al, 1998; K/DOQI Clinical Practice Guidelines for Chronic Kidney Disease, 2002a; Price et al, 2005). Given this information, spot urinary protein:urinary creatinine ratio will be used for determining proteinuria in this study for both the SELENA SLEDAI and BILAG disease activity indices.

Measurement of creatinine clearance (CrCl)/glomerular filtration rate (GFR) using timed (for example, 24-hour) urine collections is time consuming and error prone and has consistently been shown to be no more, and often less, reliable than serum creatinine based equations for the estimation of GFR (K/DOQI Clinical Practice Guidelines for Chronic Kidney Disease, 2002b). Therefore, GFR estimated by the Cockcroft-Gault formula will be used in the BILAG disease activity index, as was done in the Phase 2 and Phase 3 trials of belimumab.

### **Cockcroft-Gault Equation (Cockcroft, 1976)**

$$Cl_{cr} (\text{mL/min}) = \frac{(140 - \text{age (yrs)}) \times \text{weight (kg)}}{72 \times \text{serum creatinine (mg/dL)}} \times 0.85 \text{ if female}$$

Additional instructions regarding collection procedures are provided in the Study Procedures Manual and Central Laboratory Manual.

## **6.8.1. Guidelines for Scoring Proteinuria for SELENA SLEDAI**

The following guidelines should be followed for scoring for proteinuria in the SELENA SLEDAI disease activity index.

### **6.8.1.1. Scoring for Proteinuria for Eligibility at Screening**

In order to be assigned 4 points for proteinuria at screening, the screening spot urine proteinuria assessment must show:

- Proteinuria  $> 1 \text{ g/24 hour equivalent}$  (irrespective of previous value).

OR

- New onset or recurrent proteinuria  $> 0.5 \text{ g/24 hour equivalent}$  or a  $> 0.5 \text{ g/24 hour equivalent}$  increase above the previously documented 24-hour proteinuria or equivalent value obtained within 26 weeks of the screening value. If the screening value is  $\leq 1 \text{ g/24 hour equivalent}$  and there are no previous assessments of 24-hour proteinuria or spot urinary protein to urinary creatinine ratio available within 26 weeks for a given subject, 4 points cannot be given for proteinuria on the SELENA SLEDAI index, unless a 2nd assessment is done during the screening period of the study (ie, before Day 0).

### **6.8.1.2. Scoring for Proteinuria at Day 0 and Subsequent Study Visits**

According to the SELENA SLEDAI scoring rules, unless the proteinuria continues to rise such that it has increased by  $> 0.5$  g/24 hour equivalent at Day 0 (ie, baseline), the subject, by default, will have an improving SELENA SLEDAI score prior to treatment. Two assessments of 24-hour proteinuria (by spot urinary protein to urinary creatinine ratio) obtained in a 2 to 3 week period are unlikely to show a  $> 0.5$  g/24 hour equivalent increase except in acute renal flare. This is problematic for data analysis since the percent change in the disease activity scales are calculated from the baseline (not screening) SELENA SLEDAI score. As such, the following scoring rules will be applied:

#### **6.8.1.2.1. Scoring for a Subject with Proteinuria and 4 Points Assigned in SELENA SLEDAI**

If there is an increase from the last visit of  $> 0.5$  g/24 hour equivalent, only 4 points for proteinuria will continue to be applied (so no subject can get more than 4 points for proteinuria at any 1 time point).

If the proteinuria has not improved (ie, there has not been a decrease in proteinuria of  $> 0.5$  g/24 hour equivalent) since the previous assessment, then 4 points will continue to be assigned on the SELENA SLEDAI index at the current visit.

If proteinuria has improved (decrease of  $> 0.5$  g/24 hour equivalent or a decrease to  $\leq 0.5$  g/24 hour equivalent) from the previous visit to the current visit, then 0 points will be assigned on the SELENA SLEDAI index at the current visit.

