#### **6.8.1.2.2. Scoring for a Subject with 0 Points for Proteinuria in SELENA SLEDAI**

If the proteinuria score for SELENA SLEDAI is 0 and at the subsequent visit the assessment of 24-hour proteinuria (by spot urinary protein to urinary creatinine ratio) shows  $> 0.5$  g/24 hour equivalent increase above the previous value or the subject develops new onset of proteinuria  $> 0.5$  g/24 hour equivalent, 4 points will be assigned at this current visit.

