### **8.5.3. Secondary Efficacy Endpoints**

The major secondary efficacy endpoints include:

1. SRI response rate with the SELENA SLEDAI for scoring of proteinuria at Week 52.
2. Time to first severe flare (as measured by the modified SLE Flare Index; with SLEDAI-2K and SELENA SLEDAI as the SLEDAI criterion of the SFI).
3. Percent of subjects whose average prednisone dose has been reduced by  $\geq 25\%$  from baseline to  $\leq 7.5$  mg/day during Weeks 40 through 52, in subjects receiving greater than 7.5 mg/day at baseline.

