**Summary of Modifications and Rationale:**

1. The sample size for this study has been reduced from 816 subjects to approximately 501 subjects due to pragmatic considerations to address the study objectives for this post marketing commitment trial within a reasonable timeframe and based on updated information from studies BEL112341 (HGS1006-C1115/BLISS SC) and BEL113750 (Northeast Asia) regarding the assumed treatment differences. This modification has been made in consultation with the US Food and Drug Administration and European Medicines Agency.
2. The following has been revised in the Synopsis and Section 8:
  - The primary efficacy endpoint has been changed to the SRI response rate with the SELENA SLEDAI modified for SLEDAI-2K scoring for proteinuria. The original endpoint of the SRI with the SELENA SLEDAI scoring for proteinuria will be a major secondary endpoint. (Note: the proteinuria scoring modification occurs programmatically and does not impact the current scoring for individual subjects by the site.)
  - For other efficacy endpoints, clarification regarding the use of modified SLEDAI-2K scoring for proteinuria and SELENA SLEDAI scoring for proteinuria in the endpoint and its analysis has been added or modified accordingly.
3. The following selection criteria have been revised or clarified in the Synopsis and Section 4:
  - Revisions intended to allow more subjects to be considered for enrollment:
    - The inclusion criterion for having an unequivocally positive autoantibody test has been qualified to allow a HEp-2 immunofluorescence assay (IFA) and/or positive enzyme immunoassay (EIA) result as evidence and to allow a historically positive anti-dsDNA result to have confirmation by any validated commercial assay.
    - The exclusion criterion for prior B cell targeted therapies has been modified from a lifetime exclusion to allowance of a 1 year or more ago. Literature evidence supports that the majority of patients have largely recovered from immunosuppressive effects of B cell depletion within 1 year after treatment with B cell targeted therapy.
    - In the exclusion criterion for anti-TNF therapies, 2 other examples were added to the list.

- In the exclusion criterion for Grade 3 lab AEs, the list of exceptions was modified to allow subjects with stable Grade 3 prothrombin time (PT) secondary to anticoagulant treatment.

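### Section 6.8.1.2.1 gives two scores, 4 and 0 points, for a small fall in proteinuria to 0.5 g or less, because 'not improved' is not the complement of 'improved'

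*Protocol*

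**What the plan says.** Section 6.8.1.2 sets the proteinuria scoring rules for Day 0 and all later visits. Within it, Section 6.8.1.2.1 covers a subject who already has 4 points.

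- **Keep 4 points:** "If the proteinuria has not improved (ie, there has not been a decrease in proteinuria of" more than 0.5 g/24 hour equivalent) since the previous assessment. The parenthesis has one limb.
- **Score 0 points:** proteinuria has improved, meaning a decrease of more than 0.5 g or a decrease to 0.5 g or less, "from the previous visit to the current visit, then 0 points will be assigned on the SELENA SLEDAI index at the current visit". This definition has two limbs.

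No visible sentence in Section 6.8.1 says which rule prevails if both are met.

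Sites apply this text. Table 6-1, footnote K, instructs: "Refer to Section 6.8.1 for guidelines for scoring proteinuria for SELENA SLEDAI evaluation". Section 6.8 names the data source: "spot urinary protein:urinary creatinine ratio will be used for determining proteinuria in this study for both the SELENA SLEDAI and BILAG disease activity indices". Item 2 of the Summary of Modifications for Amendment 02 says of the SLEDAI-2K version that "the proteinuria scoring modification occurs programmatically and does not impact the current scoring for individual subjects by the site".

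Section 8.5.3 lists as the first major secondary endpoint the "SRI response rate with the SELENA SLEDAI for scoring of proteinuria at Week 52".

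**The concern.** The two sentences read as a complementary pair but are not one. For some falls, an assessor who follows the first sentence literally keeps 4 points, and one who follows the second assigns 0. The disputed item equals the 4-point reduction that SRI requires, so it can decide the SLEDAI component of response by itself.

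Three uses of the SELENA SLEDAI score are exposed:

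- SRI with SELENA SLEDAI proteinuria scoring (Section 8.5.3, item 1).
- The severe-flare endpoint, where SELENA SLEDAI is one of the two SLEDAI criteria of the flare index (Section 8.5.3, item 2).
- The renal-domain sensitivity analyses (Section 8.5.4, Organ Specific, items 1 and 2).

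Because the rule starts at Day 0, the baseline score is exposed as well as the Week 52 score.

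**Working it through.** The plan has no figure of its own to reproduce here, so the check is one of logic.

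**Definitions.** Let p be the previous value and q the current value, in g/24 hour equivalent, for a subject holding 4 points.

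- L1: p − q > 0.5.
- L2: q < p and q ≤ 0.5.
- 'Improved' (0 points) = L1 or L2.
- 'Not improved' as written (4 points) = not L1.

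**Overlap.** Both rules hold when L2 is true and L1 is not: q ≤ 0.5, q < p and p − q ≤ 0.5. When the 4 points have just been gained, p > 0.5, so the region is 0.5 < p ≤ 1.0.

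| Move (g) | Fall | 'Not improved' (4) | 'Improved' (0) |
|---|---|---|---|
| 0.8 to 0.4 | 0.4 | met | met |
| 0.6 to 0.5 | 0.1 | met | met |
| 1.0 to 0.5 | 0.5 | met | met |
| 1.0 to 0.49 | 0.51 | no | met |
| 1.1 to 0.5 | 0.6 | no | met |
| 1.2 to 0.6 | 0.6 | no | met |
| 0.9 to 0.6 | 0.3 | met | no |

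On a 0.1 g grid with p from 0.6 to 1.0 and q from 0 to 0.5 there are 5 × 6 = 30 moves. Fifteen meet L1, where only 0 points applies. The other 15 meet L2 alone, and all 15 also meet 'not improved'. For p > 0.5, the second limb therefore acts only inside the overlap. These are grid counts, not frequencies.

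**Can the case arise?** Yes. A subject at 0.8 g can hold 4 points at screening through "New onset or recurrent proteinuria" above 0.5 g (Section 6.8.1.1, with its requirement for a prior or second assessment). At a later visit the route is "or the subject develops new onset of proteinuria" above 0.5 g (Section 6.8.1.2.2).

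**Persistence.** Suppose 4 points are kept at 0.4 g.

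- Next visit 0.4 g: there is no decrease, so neither L1 nor L2 holds and 4 points continue.
- Next visit 0.3 g: the fall is 0.1 g, so both sentences are met again.
- From p ≤ 0.5 no fall can exceed 0.5 g, so the literal 'not improved' condition stays true however low the value goes.

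An overlap at an earlier visit can therefore settle the Week 52 score.

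**Effect on SRI, overlap after baseline.** Let the baseline include the 4 points, and let r be the net fall in all other items. The reduction is 4 + r under 'improved' and r under literal 'not improved'. The conditions 4 + r ≥ 4 and r ≥ 4 differ only for r = 0, 1, 2 or 3. Example: baseline 10 (4 proteinuria + 6 other), other items unchanged, Week 52 fall from 0.8 to 0.4 g. The score is 6 (reduction 4, met) or 10 (reduction 0, not met).

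**Effect on SRI, overlap at Day 0.** Let b and w be the proteinuria item at baseline and Week 52, so the reduction is b − w + r. Take a case where Week 52 proteinuria warrants 0.

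- Scored 0 at both visits: r.
- 4 kept at both visits: r, the same.
- 4 kept at Day 0 and 0 at Week 52: 4 + r, which credits a response not otherwise earned when r is 0 to 3.

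The error can therefore run in either direction.

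**Effect on severe flare.** The index in Appendix 5 counts a change in score to above 12. With other items totalling s, the two readings give s + 4 and s. They fall on opposite sides of 12 only when s is 9, 10, 11 or 12.

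**The case against.** The best reply is that the text nearly resolves itself. The sentences are framed as 'has not improved' and 'has improved', and the second names the disputed case explicitly. If the first prevailed, the second limb would do nothing. That argument stands as to intent: 0 points is meant. It does not remove the contradiction, because the parenthesis is written as a definition and assessors at many sites should not have to work out which sentence to set aside.

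It is also fair that inconsistent scoring is possible but not shown. The scale in Appendix 5 is redacted and the Study Procedures Manual is not available, and either may carry the instruction. The region is narrow, and a flip in the SLEDAI component changes SRI status only if the PGA and BILAG components are met and the subject is not already a non-responder through withdrawal, a missed visit or prohibited medication.

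A reader might go further and infer that the primary result is compromised, or that the treatment comparison is biased. The documents support neither. The primary endpoint's proteinuria item uses the programmed SLEDAI-2K modification. Nothing in the protocol gives the number of subjects in the overlap or suggests that it differs by arm.

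**Conclusion.** This is a genuine internal inconsistency in a scoring rule that sites apply. It is limited to falls of 0.5 g or less that end at 0.5 g or below, plus any points carried forward from such a fall. Confidence is high for the textual overlap and its arithmetic. The practical consequence is unquantified: it can change individual scores at baseline or Week 52 and individual status on the three SELENA SLEDAI-based uses named above, but no frequency, bias or power loss is claimed.

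Two assumptions matter. The first is that those analyses use the site-entered proteinuria item, since the protocol describes programmed scoring only for the SLEDAI-2K version. The second is that no unseen manual or appendix text already settles the case. The point is worth correcting because the correction is nearly free.

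**What to change.** Reword the parenthesis in Section 6.8.1.2.1 so that 'not improved' means neither a decrease of >0.5 g/24 hour equivalent nor a decrease to ≤0.5 g/24 hour equivalent. The overlap is then empty and every move still receives a score.

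Before unblinding, re-derive the SELENA SLEDAI proteinuria item in visit order from screening through Week 52, using the recorded spot urine ratios. Query any visit where 4 points were kept after a decrease to 0.5 g or less, and carry each correction forward to later visits and, where Day 0 is affected, into the baseline. A filter limited to previous values above 0.5 g would not be enough: a flat 0.4 g with 4 points carried forward escapes it, and the new wording alone would leave those points in place.

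The cost is one phrase, one programmed check and a few site queries. Spot urine is already collected alongside the activity scales, so no new assessment is needed.
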